#### 5.4. Assessment Time Point Identifiers

In the individual data listings, scheduled assessment time points will be identified as follows:

- Scheduled safety assessments will be identified by stage, study day, and also nominal study time point, where relevant.
- Assessments at Screening and End of Study may be identified as such for both study day and time point, as appropriate.

#### 5.5. Data Derived by Calculation

The following data fields for inclusion in the data listings will be derived by calculation as per the Clinical Data Interchange Standards Consortium (CDISC) standard:

Adverse Events:

• Treatment for adverse event, assigned as

```
Non-Treatment-Emergent if (Onset Date) < (Date of Stage A Dose)
```

[figure not shown]
Treatment for Stage A if
(Onset Date) >= (Date of Stage A Dose) &
(Onset Date) < (Date of Stage B Dose);

Treatment for Stage B if (Onset Date) >= (Date of Stage B Dose)

CONFIDENTIAL Page 12 of 27

Protocol No.: XT-150-2-0204 Sponsor: Xalud Therapeutics, Inc.

- Adverse event time since Stage B dose (in days), calculated as
   (Onset Date) (Date of Stage B Dose) if (Onset Date) >= (Date of Stage B
   Dose)
- Adverse event time since Stage B dose is Not Applicable if if (Onset Date) < (Date of Stage B Dose)

- Adverse event duration (in days), calculated as (Resolution Date

  – Onset Date)

Safety Assessments Change from Baseline:

Baseline for vital signs and clinical laboratory parameters will be the most recent
assessment prior to first dose [which may be an unscheduled assessment, a repeat of
a scheduled Baseline assessment, or the screening assessment if separate Baseline
assessments are not performed]

Clinical Safety Laboratory Assessments:

- If a clinical laboratory result is above the upper limit of normal, then Out of Range flag will be set to "H"
- If a clinical laboratory result is below the lower limit of normal, then Out of Range flag will be set to "L"
- Clinical Laboratory parameters that are outside the reference range and medically assessed as clinically significant will be identified as "Abnormal CS"
- Clinical Laboratory parameters that are outside the reference range and not medically assessed as clinically significant will be identified as "Abnormal NCS"

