13.4 Safety Analyses

All participants who receive any amount of study drug (Safety Population) will be included in the safety analyses.

Safety will be evaluated by presenting summaries of AEs and vital signs. Safety variables will be tabulated by treatment group.

Adverse events will be graded using the CTCAE v5.0 and will be coded using the Medical Dictionary of Regulatory Affairs (MedDRA®), Version 18 or higher. AEs will be collected for each participant from the signing of the informed consent through the last study visit on Day 360.

A treatment-emergent adverse event (TEAE) is defined as an AE that occurs during or after study drug administration. The incidence of TEAEs will be presented by system organ class (SOC) and preferred term (PT), by SOC, PT, and relationship to the study drug administration, and by SOC, PT, and severity. In addition, the incidence of serious TEAEs and TEAEs leading to discontinuation of study drug will be presented by SOC and PT.

Descriptive statistics for clinical laboratory test results, and vital signs, and for changes from Baseline, will be presented by time point. Baseline is defined as the measurement closest to, but prior to, the administration of study drug. Incidences of potentially clinically significant clinical laboratory results, and vital signs, as defined in the SAP, will also be summarized by time point. A summary of abnormal physical examination findings will also be presented.

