#### 8.2. Safety Data Presentation and Analysis

All clinical safety and tolerability data will be listed for each subject.

Safety data will be summarized using descriptive statistics. Where summaries include changes from baseline, the relevant baseline value will be determined as described in Section 5.5 above.

All adverse events will be listed using MedDRA terms, as coded per the Data Management Plan. The number and percentage of subjects with at least one treatment emergent AE and the number of treatment emergent AEs reported will be summarized by dose level or treatment, grouped according to system organ class and preferred term, using descriptive statistics. The order for system organ class will be according to the Internationally Agreed Order, as per the guidance document MedDRA® *Data Retrieval and Presentation: Points to Consider*, specific to the MedDRA version used for this study. Summaries of TEAEs will also be presented by severity (graded according to the NCI CTCAE version 5.0) and by relationship to investigational product. In these summaries, subjects will be counted at most once per MedDRA term, for the AE of highest severity or least favorable relationship. Summaries will also be presented for SAEs and for AEs leading to study withdrawal.

Clinical laboratory parameters for hematology, serum chemistry, and coagulation will be listed. Summaries of reported results, including changes from baseline and medical

CONFIDENTIAL Page 16 of 27

Protocol No.: XT-150-2-0204 Sponsor: Xalud Therapeutics, Inc.

assessments, will be presented by treatment group and study timepoint. Individual subject profiles will be presented for any laboratory parameters with at least one post-dose value outside the laboratory's reference ranges and deemed clinically significant.

Vital signs will be listed and summarized by dose level / treatment and study timepoint. A summary of changes from pre-dose baseline will also be presented.

Changes in physical examination findings over time will be listed by body system for each subject. It is noted that any untoward findings identified on physical examinations after the administration of the first dose of study medication will be captured as an adverse event if those findings meet the definition of an adverse event as defined in the protocol.

Injection site examinations will be listed and summarized by dose level / treatment and study timepoint.

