#### 9.3. Efficacy Analysis

All inferential analyses of efficacy will be based on the first 180 days after dose administration (Stage A) and on the analysis of time from Day 0 until patient request for a second injection.

CONFIDENTIAL Page 18 of 27

Final 2.0, 11 Oct 2021

Sponsor: Xalud Therapeutics, Inc.

Protocol No.: XT-150-2-0204

[figure not shown]
For the statistical analysis of the primary efficacy endpoint, a logistic regression (response: 30% improvement at Day 180 (yes/no)) will be performed to compare 150 µg XT-150 with placebo and 450 µg XT-150 with placebo statistically. The model will include a fixed effect for treatment and the subject's baseline WOMAC pain score as a covariate. From this model, the 150 µg XT-150 to placebo and 450 µg XT-150 to placebo odds ratio of reduction and its two-sided 95% CI will be calculated. In this analysis, a subject who does not provide a response at Day 180 will be considered a non-responder (i.e., improvement will be set to "no").

In the event that one or more treatment arms has no responders, which would cause numerical difficulties in the logistic regression model, the statistical analysis will add 2 successes and 2 failures to each treatment group. This based on the recommendation in Agresti and Caffo, "Simple and Effective Confidence Intervals for Proportions and Differences of Proportions Result from Adding Two Successes and Two Failures," The American Statistician, Vol. 54, No. 4 (Nov., 2000), pp. 280-288.

The change from baseline in WOMAC Function Score will be analyzed using a repeated measures model including fixed effects for treatment (i.e., 150 µg XT-150, 450 µg XT-150, placebo), study day (i.e., Day 7, 30, 60, 90, 120, 150, 180) and treatment by study day interaction. In addition, the subject's baseline score will be included as a covariate. From the model, the treatment differences between 150 µg XT-150 and placebo, and 450 μg XT-150 and placebo will be estimated for the average effect of the first 180 days after dose administration (i.e., Stage A). Additionally, p-values and corresponding two-sided 95% confidence intervals will be provided.

The change from baseline in WOMAC Pain Score will be analyzed similarly.

Change from baseline in total and individual BPI, change from baseline in KOOS, and change from baseline in the patient response will be analyzed similarly.

CONFIDENTIAL Page 19 of 27

Final 2.0, 11 Oct 2021

Protocol No.: XT-150-2-0204 Sponsor: Xalud Therapeutics, Inc.

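### SAP 5.5 credits adverse events to Stage A treatment until an optional second injection, with no Day 180 limit and no rule for participants never re-injected; if the TEAE tables use this field, the arms may be compared over unequal follow-up

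*SAP*

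**What the plan says.** SAP 5.5 derives a treatment label for each adverse event. The first value is "Non-Treatment-Emergent if (Onset Date) < (Date of Stage A Dose". An event on or after the Stage A dose is credited to Stage A treatment while "Onset Date) < (Date of Stage B Dose", and from the Stage B dose onward it is credited to Stage B treatment. The lead-in to the section reads "The following data fields for inclusion in the data listings will be derived by calculation".

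The Stage B dose is the participant's choice. Protocol Table 1 (footnote k) allows it at the Day 180 visit, and Protocol Table 2 (footnote c) and SAP 4.4 allow it up to Day 330. Protocol 13.4 states that "AEs will be collected for each participant from the signing of the informed consent through the last study visit on Day 360".

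SAP 8.2 tabulates "The number and percentage of subjects with at least one treatment emergent AE" and says that "treatment emergent AEs reported will be summarized by dose level or treatment". No time window, stage split or person-time is visible there. For efficacy, SAP 9.3 does set a limit: "All inferential analyses of efficacy will be based on the first 180 days after dose administration (Stage A", and also "on the analysis of time from Day 0 until patient request for a second injection".

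SAP 4.1 announces an analysis of both efficacy and safety at six months. The visible text gives no AE cut-off for it.

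**The concern.** The end of the period credited to Stage A is set by a decision taken after randomisation. A completer who is re-injected at Day 180 contributes 180 days. One who never is would contribute up to 360 days, if the rule is read as running to the last visit. The text does not say even that much, because a comparison with a missing Stage B date has no defined answer.

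Safety and tolerability of a single dose is the primary objective (Protocol 5.0), and Stage A is the only placebo-controlled period. If the tables use this field and one arm requests the second injection more often or earlier, the other arm has longer to accumulate events. Its crude TEAE percentage then rises with no difference in risk. No document predicts such a difference, but SAP 9.3 analyses time to request as an efficacy outcome, so the plan itself allows that it may vary by arm. Safety is descriptive, so the stake is how the table is read, not a test.

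**Working it through.** **Inputs from the documents.** The Stage A window runs from the Stage A dose to the Stage B dose (SAP 5.5). The second injection is possible from the Day 180 visit, ±7 days, to Day 330 (Protocol Tables 1 and 2). AEs are collected to Day 360 (Protocol 13.4). There are 90 participants per arm (Protocol 13.1). The documents give no TEAE incidence, uptake, timing or hazard shape, so there is no plan figure to reproduce.

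**Assumptions.** The AE hazard is the same in all arms. TEAE incidence by Day 180 is p = 30% or 50%. Uptake u is 90% on placebo and 70% on XT-150, as if uptake tracked the planning non-response rates. Participants not re-injected are followed to Day 360, except where stated.

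**Credited follow-up.** Mean = u·T + (1−u)·360, with T the day of re-injection. At T = 180: 0.9×180 + 0.1×360 = 198 days on placebo and 0.7×180 + 0.3×360 = 234 days on XT-150. Between individual completers the ratio can reach 360/180 = 2.

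**Crude TEAE percentage.** Incidence = u·F(T) + (1−u)·F(360), with F(t) = 1 − exp(−H(t)) and H = −ln(1−p).

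- Constant hazard: H(t) = H·t/180, so F(360) = 51% (p = 30%) or 75% (p = 50%). Example at p = 30%, T = 180: 0.9×30 + 0.1×51 = 32.1% against 0.7×30 + 0.3×51 = 36.3%.
- Front-loaded hazard: 0.8H is used by Day 30, then 0.2H/150 per day. This is nearer to the injection-site reactions described in Protocol 4.4.2.
- Spread timing: F(T) is averaged evenly over Days 180 to 330.

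| Hazard | Re-injection | p = 30%: placebo vs XT-150 | Gap (points) | p = 50%: placebo vs XT-150 | Gap (points) |
|---|---|---|---|---|---|
| Constant | Day 180 | 32.1 vs 36.3 | 4.2 | 52.5 vs 57.5 | 5.0 |
| Constant | Spread | 40.6 vs 42.9 | 2.3 | 63.3 vs 65.9 | 2.6 |
| Front-loaded | Day 180 | 30.57 vs 31.72 | 1.15 | 50.77 vs 52.30 | 1.53 |
| Front-loaded | Spread | 32.77 vs 33.43 | 0.66 | 53.75 vs 54.62 | 0.87 |

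**Withdrawal.** Suppose half of those not re-injected leave at Day 180. F(360) is then replaced by the mean of F(180) and F(360), which is 40.5% or 62.5% at constant hazard. With Day 180 timing the gaps become 31.05 vs 33.15 (2.1 points) and 51.25 vs 53.75 (2.5 points). With spread timing they fall to 0.2 and 0.1 points.

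**Null case and direction.** Equal uptake, timing and withdrawal give a gap of zero. Exchanging the two uptake figures reverses the sign.

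**Yardstick.** The standard error of a difference is √(2p(1−p)/90) = 6.8 points at 30% and 7.5 at 50%.

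**Wider uptake gap.** With 80% vs 40% uptake, p = 40%, constant hazard and Day 180 timing, F(360) = 64%. The percentages are 0.8×40 + 0.2×64 = 44.8% and 0.4×40 + 0.6×64 = 54.4%, a gap of 9.6 points. That exceeds the standard error of √(2×0.4×0.6/90) = 7.3 points.

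**After the fix.** The visit window allows re-injection from Day 173. If every re-injection fell on that day, the 20-point uptake gap would leave 0.2×(F(180) − F(173)) = 0.20 to 0.27 points at constant hazard.

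**The case against.** The strongest objection is that nothing visible shows the tables use this field. SAP 5.5 is introduced for listings. The AE imputation rules that follow in SAP section 5 are written expressly for the summaries, which suggests that the SAP says so when it means the tables. The table list in Appendix 2 and the body of 11.1 are not in the public copy, and SAP 4.1 announces a six-month safety analysis whose window may be defined there. This stands, and it keeps the point conditional. It does not dispose of it. SAP 8.2 itself refers to 5.5 for the baselines used in summaries, so the listings lead-in does not confine 5.5 to listings. Some participants receive two treatments, so a table by treatment needs an attribution rule, and 5.5 holds the only one visible.

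It can also be argued that crediting an event to the latest dose is a reasonable convention, that using all single-dose follow-up suits a single-dose objective, and that the 180-day limit in 9.3 concerns inference only. All three are fair. The convention rightly keeps events after active re-injection out of the Stage A column. It does not give the arms a common window.

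Finally, the size rests on stacked assumptions, and Protocol 7.4.1 lists perceived lack of benefit and loss to follow-up among the withdrawal reasons. The working shows that withdrawal can shrink the gap almost to nothing.

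**Conclusion.** The point holds in conditional form. The 5.5 rule has no Day 180 bound and does not cover participants without a Stage B dose date. If the 8.2 tables use it, the placebo comparison covers unequal follow-up whenever uptake or timing of the second injection differs by arm. Under the stated assumptions the artefact is about 0.7 to 5.0 points without withdrawal. At constant hazard it is 0.1 to 2.5 points if half of the non-re-injected leave at Day 180. All of these are below one standard error. Only a wider uptake gap, which no document suggests, would exceed it.

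A reader might infer that the placebo-controlled safety comparison is biased, or biased against XT-150. The documents do not support that: use of the field in the tables is unconfirmed, no uptake figures are given, and the direction depends on which arm re-injects more. Nor can a reader conclude that no six-month safety cut exists, since SAP 4.1 points to one. This is an inexpensive improvement to a descriptive table, not a demonstrated flaw. Confidence is medium.

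**What to change.** In SAP 5.5 and 8.2:

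- Base the placebo-controlled TEAE comparison on AEs with onset up to the earlier of the second injection and a fixed study Day 180, not the visit date.
- Show later AEs that precede any second injection as a separate single-dose category, with person-time by arm. For 90% vs 70% uptake at Day 180 without withdrawal, that is 90×0.1×180/365.25 = 4.4 and 90×0.3×180/365.25 = 13.3 person-years.
- Keep AEs after the second injection separate, as 5.5 already does.
- State that participants with no Stage B dose date stay in the single-dose categories until their last follow-up.

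If a Day 180 safety cut already exists in text outside the public copy, align 5.5 and 8.2 with it. The SAP Addendum says that the database is locked and unblinded, so any table added now should be labelled post hoc.

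The cost is SAP wording, one derived category and one table, all from dates already collected. The downside is fewer events in the main comparison. The number of participants moved is 90×(incidence − p). At constant hazard this is about 2 placebo and 6 to 7 XT-150 participants of 90 with re-injection at Day 180, or about 10 to 12 and 12 to 14 if spread over Days 180 to 330. It is fewer if the hazard is front-loaded. Those events stay in the report, in the separate category.

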- f. Participant assessment will be recorded in response to the question: "Considering all the ways the OA in your knee affects you, how are you doing today?" on a scale of 1 to 5, 5 being worst
- i. Women of child-bearing potential
- Verify that the participant meets all study inclusion and exclusion criteria before enrollment as close to study drug dosing as
 possible.
- k. Participant will receive a single, 1-mL dose of study drug into the intra-articular space of the knee on Day 0. Participant may elect a second injection on Day 180 (enters Stage B) after efficacy assessments have been recorded.
- A telephone call documenting safety and efficacy assessments may be used for participants unable to physically attend follow
 up visits due to COVID-19 infection or corona virus exposure concerns

Table 2. Schedule of Assessments and Procedures - Stage B

Scheduled Event	Follow up Visit Day ^d							
	210	240	270	300	330	360		
	(±7)	(±7)	(±7)	(±7)	(±7)	(±7)		
KOOS/WOMAC	X	X	X	X	X	X		
BPI	X	X	X	X	X	X		
Patient response to OA question	X	X	X	X	X	X		
	X	X	X	X	X	X		
						X		
Brief physical examination	X	X	X	X	X	X		
Record height and weight, calculate BMI						X		
Vital signs	X	X	X	X	X	X		
Clinical exam of the treated joints	X	X	X	X	X	X		
Record AEs	X	X	X	X	X	X		
Record SAEs	X	X	X	X	X	X		
	X	X	X	X	X	X		
Record concomitant medications	X	X	X	X	X	X		
Serum for anti-IL-10 antibody assessments						X		
Serum pregnancy test ^b						X		
Administer study drug ^c	X	X	X	X	X			

Footnotes to Table 2

- b. Women of child-bearing potential
 c. Participants may elect for one (1) XT-150 IA injection into the Index Knee at any point during Stage B up to Day 330, inclusive. The XT-150 dose (150 μg or 450 μg) will be randomly assigned.
- d. A telephone call documenting safety and efficacy assessments may be used for participants unable to physically attend follow up visits due to COVID19 infection or corona virus exposure concerns

$\mathbf{T}A$	BLE OF CONTENTS	
PF	OTOCOL SYNOPSIS	3
TA	BLE OF CONTENTS	10
	ST OF ACRONYMS, ABBREVIATIONS AND DEFINITIONS (
	RMS	
	CKGROUND AND RATIONALE	
4.1	XT-150	
4.2		
4.3	1	
4.4		

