10.3 Adverse Events

Medical history will be collected for all participants at the time of informed consent. After consent, all AE's will be collected. The Investigator will assess all AEs and SAEs and will record the following information on the appropriate CRF page:

- Date of onset
- Date of resolution or stabilization
- Severity
- Relationship to study drug
- Action taken with study medication

Medically indicated laboratory tests (emergency or unscheduled tests) should be conducted at the local laboratory. The Investigator should employ best medical judgment in determining how to manage AEs and SAEs. Any questions regarding AE or SAE management should be directed to the Medical Monitor.

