10.6.2 Severity

All AEs will be graded for severity to describe the maximum intensity of the AE based on Common Terminology Criteria for Adverse Events (CTCAE) criteria (version 5.0). For purposes of consistency, these intensity grades are defined in Table 6.

Table 6. Guidelines for Severity Assessments

Grade 1	Mild; asymptomatic or mild symptoms; clinical or diagnostic observations only; intervention not indicated
Grade 2	Moderate; minimal, local or non-invasive intervention indicated; limiting age-appropriate instrumental activities of daily living (e.g., preparing meals, shopping for groceries or clothes, using the telephone, managing money)
Grade 3	Severe or medically significant but not immediately life-threatening; hospitalization or prolongation of hospitalization indicated; disabling; limiting self-care activities of daily living (bathing, dressing and undressing, feeding self, using the toilet, taking medications, and not bedridden)
Grade 4	Life-threatening consequences; urgent intervention indicated
Grade 5	Death related to adverse event

These criteria, in addition to good clinical judgment, should be used as a guide for determining the causal assessment. If the event is believed to be unrelated to study drug administration, then an alternative explanation should be provided.

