#### 4.4. Study Treatment

Treatments in Stage A:

- Placebo (1 mL phosphate-buffered saline for injection)
- 150 μg XT-150 (1 mL)
- 450 μg XT-150 (1 mL)

Treatments in Stage B:

- 150 μg XT-150 (1 mL)
- 450 μg XT-150 (1 mL)

At enrolment in Stage A, participants will be randomly enrolled into 1 of 6 treatment sequences (approximately 45 participants/ group) to receive one of 3 treatments in Stage A, and, optionally, one of 2 treatments in Stage B.

CONFIDENTIAL Page 8 of 27

Final 2.0, 11 Oct 2021

Protocol No.: XT-150-2-0204 Sponsor: Xalud Therapeutics, Inc.

At any time in Stage B up to Day 330, inclusive, participants can elect for a single injection to the knee dosed in Stage A (Index Knee). The second injection dose will be either 150  $\mu$ g or 450  $\mu$ g XT-150, according to the randomized treatment sequence allocated on enrolment in Stage A. There will be no placebo comparator in Stage B.

Treatment sequences for randomization:

- XT-150 (150 μg) in Stage A, followed by XT-150 (150 μg) in Stage B
- XT-150 (150 μg) in Stage A, followed by XT-150 (450 μg) in Stage B
- XT-150 (450 μg) in Stage A, followed by XT-150 (150 μg) in Stage B
- XT-150 (450 μg) in Stage A, followed by XT-150 (450 μg) in Stage B
- Placebo in Stage A, followed by XT-150 (150 μg) in Stage B
- Placebo in Stage A, followed by XT-150 (450 μg) in Stage B

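### SAP 5.5 attributes adverse events by onset date alone, so an event that worsens after an injection can be counted at its worst grade under the earlier treatment or left out of the TEAE tables

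*SAP*

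**What the plan says.** SAP 5.5 sorts adverse events into three classes. Before the first injection the rule is "Non-Treatment-Emergent if (Onset Date) < (Date of Stage A Dose". Events from the Stage A dose up to the Stage B dose go to the Stage A treatment. From the second injection the rule is "Treatment for Stage B if (Onset Date) >= (Date of Stage B Dose". Onset date and dose dates are the only inputs.

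Protocol 13.4 gives the definition behind these classes: "A treatment-emergent adverse event (TEAE) is defined as an AE that occurs during or after study drug administration". It does not mention a pre-existing event that gets worse.

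On grading, Protocol 10.6.2 says "All AEs will be graded for severity to describe the maximum intensity of the AE". The items that Protocol 10.3 lists for the CRF are onset date, "Date of resolution or stabilization", severity, relationship and action taken. No date of grade change is listed. SAP 8.2 then summarizes TEAEs by severity and relationship, taking the worst per subject and MedDRA term.

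Two design features make the case reachable:

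- Collection starts before dosing. Protocol 13.4 states "AEs will be collected for each participant from the signing of the informed consent through the last study visit on Day 360", and screening may run for up to 30 days.
- The second injection is optional and its date is chosen by the participant. Protocol Table 2, footnote c, says "Participants may elect for one (1) XT-150 IA injection into the Index Knee at any point during Stage B up to Day 330, inclusive", and Protocol 9.6 also offers it at the Day 180 visit. It is always active drug (SAP 4.4).

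**The concern.** Confirming safety and tolerability is the trial's primary objective, and the TEAE tables are its main output. An onset-only rule works for events that are new after an injection. It does not work for an event that is already present, mild, and then rises in grade after an injection. The rise is the post-injection information, but the rule looks only at when the event began, while the recorded grade is the worst it reached.

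Two results follow if such an event stays a single record. If it began before Day 0, it is classed as non-treatment-emergent whatever happens after dosing. If it began in Stage A and worsened after the second injection, its worst grade is credited to the Stage A treatment. In a placebo-first participant that moves a worsening after the first XT-150 exposure into the placebo column. The relationship assessment moves with it, because that field does not reassign an event to another treatment.

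Grade is not incidental in this trial: Protocol 10.2 defines its events of noted interest by CTCAE grade. Elsewhere the SAP is conservative. In its missing-data rules (SAP 5.6), unknown severity becomes Grade 3, unknown relationship becomes related, and an event of unknown onset counts as treatment-emergent unless onset before dosing can be confirmed. The onset-only rule can work in the opposite direction, and no visible text explains why.

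**Working it through.** The plan states no figure on this point, so there is none to reproduce. The check applies the SAP 5.5 rule literally to hypothetical event histories, then counts the sequences in which the label changes.

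**Step 1: the rule on five histories.** Day numbers and grades are assumed for illustration; Day 0 is the Stage A dose.

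| History | Second injection | Label under SAP 5.5 | Label by date of worsening |
|---|---|---|---|
| Onset Day −10 at Grade 1, Grade 3 on Day 2 | not relevant | Non-treatment-emergent | Stage A |
| Onset Day 170 at Grade 1, Grade 3 on Day 185 | Day 180 | Stage A | Stage B |
| Onset Day 300 at Grade 1, Grade 3 on Day 335 | Day 330 | Stage A | Stage B |
| Onset Day −10 at Grade 1, Grade 3 on Day 185 | Day 180 | Non-treatment-emergent | Stage B |
| Control: new onset on Day 185 | Day 180 | Stage B | Stage B |

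The new-onset control is labelled correctly. In all four worsening histories the Grade 3 goes to the earlier treatment or outside the TEAE tables.

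**Step 2: which sequences get a wrong treatment label.** SAP 4.4 says "participants will be randomly enrolled into 1 of 6 treatment sequences (approximately 45 participants/ group". Take an event with onset in Stage A, on or after the Stage A dose, that worsens after the second injection:

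| Sequence (Stage A, then Stage B) | Treatment charged | Treatment given before the worsening | Error |
|---|---|---|---|
| Placebo, then 150 µg | Placebo | 150 µg | Treatment |
| Placebo, then 450 µg | Placebo | 450 µg | Treatment |
| 150 µg, then 450 µg | 150 µg | 450 µg | Dose |
| 450 µg, then 150 µg | 450 µg | 150 µg | Dose |
| 150 µg, then 150 µg | 150 µg | 150 µg | Stage only |
| 450 µg, then 450 µg | 450 µg | 450 µg | Stage only |

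- Placebo charged: 2 × 45 = 90 of 270 randomized.
- Other XT-150 dose charged: 2 × 45 = 90 of 270.
- Any wrong treatment label: 90 + 90 = 180 of 270, or 4 of 6 sequences.
- Stage wrong but dose right: 2 × 45 = 90 of 270.

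These are ceilings on the participants to whom the rule could apply. Only those who elect the second injection, have an event ongoing at it, and then worsen in grade are affected. The documents give none of these shares.

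**Step 3: onset before the Stage A dose.** Here the class is non-treatment-emergent in every arm alike. The case is confined to events that begin in the screening window of up to 30 days.

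**The case against.** The strongest objection is that the error requires the worsened event to remain one record. Protocol 10.6.2 and 10.3 do not say whether it does. That is settled in the CRF, its completion instructions or the data management plan, none of which is available here. SAP 5.5 is also incompletely reproduced, and the list of planned tables in SAP Appendix 2 is blank, so the columns of the adverse event tables cannot be seen. The SAP 5.5 fields are introduced as listing fields, and SAP 8.2 says only that summaries are by dose level or treatment. This objection stands as a condition on the conclusion. It does not supply a worsening rule.

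Other text narrows the affected events. Protocol 10.5.1 keeps osteoarthritis-related events out of adverse event recording unless they are serious, which removes a condition likely to be present at both injections. Protocol 10.8.1 requires injection-site signs of infection or inflammation to be recorded as adverse events. SAP 8.2 has untoward physical examination findings after the first dose captured as events if they meet the definition. Some post-injection changes may therefore enter as new records, but neither provision says that a worsened existing event becomes one.

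Two stronger readings are tempting. A reader might put a count on the problem by assuming that 10–30% of participants have an event ongoing at injection, giving 0.10 × 90 = 9 to 0.30 × 90 = 27 per arm. That share is an assumption, and it counts ongoing events rather than events that worsen, so it does not measure misclassification. A reader might also infer that the rule favours XT-150 throughout. It does so in the two placebo-first sequences. In the other four, worsening after the second injection is still charged to an XT-150 dose, and exclusion of events that begin before Day 0 applies to all arms.

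**Conclusion.** The point holds conditionally. As written, SAP 5.5 and Protocol 13.4 have no means of crediting a worsening to the injection it follows. With maximum-grade recording, an event that stays one record carries its worst grade to the earlier treatment, or is excluded from the TEAE tables if onset preceded the Stage A dose. For worsening after the second injection, the treatment label is wrong in 4 of 6 sequences, split evenly between placebo and the other XT-150 dose.

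The conclusion rests on two assumptions: that no CRF convention outside these documents opens a new record on worsening, and that the adverse event tables use the SAP 5.5 labels. The number of misclassified events is unknown. It is limited to participants who elect the second injection or have an event starting during screening, and it excludes osteoarthritis-related events that are not serious.

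Severity is should-fix. The stated rule gives a wrong result on the primary objective and is cheap to correct. But the safety summaries are descriptive, the size is unknown and the mechanism depends on an unseen convention, which does not support calling it an essential correction.

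**What to change.** - In SAP 5.5 and Protocol 13.4, define a TEAE as an event with onset on or after an injection, or an event already present whose CTCAE grade increases after an injection.
- Credit the increase to that injection as a new record dated at the increase, and keep the earlier grade under the earlier period.
- Instruct sites to open a new adverse event line on such an increase. If sites already do this, state the convention in the SAP.
- For data already collected, review events ongoing at an injection against existing dated severity entries or source records. This matters because the SAP addendum's introduction says the database had been locked and unblinded by the time it was written, so a new site instruction may come too late.

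The cost is revised wording in two documents, one CRF-completion instruction, a change to the derivation and a limited record review. TEAE counts will rise slightly.
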